1.2. Study Design

Early Termination Note: Due to the Sponsor's decision to stop screening of new participants as a result of enrollment challenges, fewer than 60 participants will be enrolled in the study. The end of study will occur after all enrolled participants have completed the Week 20 visit or discontinued study intervention prior to Week 24, and all participants have completed their final efficacy and safety visits per the SoA.

CNT01959LUN2001 is a randomized, double-blind, placebo-controlled, parallel, multicenter, interventional Phase 2 study in participants aged 18 to 75 (inclusive) with active lupus nephritis (LN). The total duration of the study is up to 68 weeks: a \leq 8-week screening period (rescreening is permitted once per participant), a 48-week double-blind treatment period, and a 12-week safety follow-up period after the last dose (8 weeks after the final efficacy visit). Participants starting mycophenolate mofetil (MMF) / mycophenolic acid (MPA) at/or within 2 weeks of screening may extend screening for up to 2 additional weeks.

Efficacy, safety, PK, immunogenicity, and biomarkers (where local regulations permit) will be assessed according to the SoA in the study protocol. An optional pharmacogenomic blood sample will be collected from participants who consent to the collection of these samples (where local regulations permit).

The primary efficacy analysis will be performed after all participants have completed Week 24 efficacy assessments (or discontinued). Additional secondary endpoints will be completed at Week 24 and Week 52.

Every reasonable effort should be made to keep concomitant medications stable as defined in the protocol. Beginning at the screening visit, all concomitant therapies and all changes in concomitant therapies should be recorded throughout the study.

Key safety assessments include AEs, clinical laboratory tests (hematology and chemistry), systolic and diastolic blood pressures over time, monitoring for hypersensitivity reactions, AEs temporally

associated with infusion, injection-site reactions, suicidality assessment, and early detection of active tuberculosis.

Participants who complete the Week 52 visit and achieve a CRR, may have the option to participate in a LTE study.

Due to study termination, only one DBL will occur at the end of study.

An external, independent Data Monitoring Committee (DMC) will be commissioned for this study. The DMC will review unblinded data on a periodic basis to ensure the safety of participants enrolled in the study. The main focus of the DMC will be on reviewing interim unblinded safety data, but the DMC may also review efficacy data needed to ensure the full benefit:risk profile for guselkumab. The DMC responsibilities, authorities, and procedures will be documented in a separate DMC charter.

NUMBER OF PARTICIPANTS

A target of approximately 60 participants will be randomly assigned in a 1:1 ratio to study intervention in this study, with approximately 30 participants planned per intervention group.

INTERVENTION GROUPS AND DURATION

Participants in the study will maintain their standard-of-care treatment of mycophenolate mofetil (MMF)/mycophenolic acid (MPA) and background glucocorticoid. Participants' glucocorticoid dose will be tapered.

Participants will be randomized to 1 of 2 intervention groups in a 1:1 ratio as described below:

- Guselkumab: Participants will receive guselkumab 400 mg intravenously (IV) at Weeks 0, 4 and 8 (ie, 3 IV doses) and guselkumab 200 mg subcutaneous (SC) every 4 weeks (q4w) from Week 12 through Week 48.
- Placebo: Participants will receive placebo IV at Weeks 0, 4 and 8 (ie, 3 IV doses) and placebo SC q4w from Week 12 through Week 48.

Participants will be stratified by geographic region (North America, Latin America, Asia Pacific and Europe) and Urine Protein to Creatinine Ratio (UPCR) level (<3 mg/mg and ≥ 3 mg/mg).

[figure not shown]
Participants will remain on their assigned treatment through Week 48. All participants will receive an IV infusion (either active or placebo) at Weeks 0, 4, and 8 and 2 SC injections (either active or placebo) at Week 12 then q4w through Week 48.

Eligible participants will continue to receive the same study intervention q4w (placebo or guselkumab) in the LTE. The first dose in the LTE will be at Week 52.

The study participants will remain blinded throughout the study (including the LTE). Due to study termination, one DBL for the study will occur at the end of study. The end of study will occur after all enrolled participants have completed the Week 20 visit or discontinued study intervention prior to Week 24, and all participants have completed their final efficacy and safety visits per the SoA.

The study schema is provided in [Figure 1](#).

Figure 1: Schematic Overview of the Study

Abbreviations: CRR=complete renal response; DBL=database lock; F/U=follow-up; LTE=long-term extension; IV=intravenous; MSE=major secondary endpoint; N=number of participants; PE=primary endpoint, R=randomization; SC=subcutaneous; SOC=standard-of-care.

2. STATISTICAL HYPOTHESES

The primary hypothesis of this study is that guselkumab plus standard-of-care is superior to placebo plus standard-of-care in participants with active LN as measured by the proportion of participants inducing at least a 50% reduction of proteinuria with protocol specified steroid tapering regimen at Week 24.

3. SAMPLE SIZE DETERMINATION

Early Termination Note: Due to the Sponsor's decision to stop screening of new participants as a result of enrollment challenges, fewer than 60 participants will be enrolled in the study. The end of study will occur after all enrolled participants have completed the Week 20 visit or discontinued study intervention prior to Week 24, and all participants have completed their final efficacy and safety visits per the SoA.

The sample size section below is the originally planned sample size.

Approximately 60 participants are planned to be randomized into the study.

The study will be considered a success if the 1-sided p-value for testing the difference in proportion of participants with $\geq 50\%$ decrease in proteinuria between the guselkumab and placebo

intervention groups based on a logistic mixed effect repeat measurement longitudinal model is less than a 1-sided alpha level of 10%.

Table 1 shows the sensitivity, with respect to various assumed between group difference, of estimated power to detect a difference in proportions of participants with $\geq 50\%$ decrease in proteinuria between the guselkumab and placebo intervention groups at Week 24.

Table 1: Power to Detect Difference in Proportions of Participants with $\geq 50\%$ Decrease in Proteinuria Between the Guselkumab and Placebo Intervention Groups at Week 24

Difference in proportion of participants with $\geq 50\%$ decrease in proteinuria between the intervention groups	Power (%)
20%	56.34
25%	79.61
30%	89.84
35%	96.08

Notes:

- Proportion of placebo participants with $\geq 50\%$ decrease in proteinuria is assumed to be 49%.
- Power calculation is based on 1-sided α of 0.10.
- Total sample size is 60.

If the proportion of placebo participants with $\geq 50\%$ decrease in proteinuria is 49%, and the difference in proportion between the intervention groups is 30%, a total sample size of 60 with a 1-sided alpha of 10% will provide approximately 90% power for success.

4. POPULATIONS (ANALYSIS SETS) FOR ANALYSIS

Early Termination Note: Due to the Sponsor's decision to stop screening of new participants as a result of enrollment challenges, fewer than 60 participants will be enrolled in the study. The end of study will occur after all enrolled participants have completed the Week 20 visit or discontinued study intervention prior to Week 24, and all participants have completed their final efficacy and safety visits per the SoA.

To adapt this study change, one new analysis set is added for the efficacy analysis.

The populations for analysis are defined in Table 2 below.

Table 2: Description of analysis sets used to analyze the data in the study.

Analysis Sets	Description
Enrolled	All participants who sign the ICF
Randomized	The randomized analysis set includes all participants who were randomized in the study.
Full Analysis Set (FAS)	The FAS includes all randomized participants who received at least 1 dose of any study intervention.
Full Analyses Set for Week 52 (FASC52)	The FASC52 includes all randomized participants who received at least 1 dose of any study intervention and have the opportunity to complete the Week 52 visit prior to study termination
Safety	The safety analysis set includes all participants who received at least 1 dose of any study intervention.

Table 2: Description of analysis sets used to analyze the data in the study.

Analysis Sets	Description
Pharmacokinetics Analysis Set	The PK analysis set is defined as participants who received at least 1 dose of any active study intervention and have at least 1 valid post initial dose blood sample drawn for PK analysis.
Immunogenicity Analysis Set	The immunogenicity analysis set is defined as all participants who received at least 1 dose of active study intervention and have at least 1 post initial dose sample collection.
Biomarker Analysis Set	The biomarker analysis set is defined as participants who received at least 1 dose of any study intervention and have at least one sample for biomarker analysis

5. STATISTICAL ANALYSES

Early Termination Note: Due to the Sponsor's decision to stop screening of new participants as a result of enrollment challenges, fewer than 60 participants will be enrolled in the study. The end of study will occur after all enrolled participants have completed the Week 20 visit or discontinued study intervention prior to Week 24, and all participants have completed their final efficacy and safety visits per the SoA.

The statistical analyses section below is the originally planned analyses section. The analyses to be summarized in the study CSR will be noted at the beginning of each section below. For efficacy analyses, only the primary and secondary endpoints will be included in the CSR. Selected PK and biomarker analyses will be included in the CSR. All safety information collected will be summarized in the CSR. See below for details.

5.1. General Considerations

The statistical analyses will include all analyses from Week 0 through Week 60 (the final safety follow-up).

In general, baseline is defined as the last observation prior to or at the time of the first study agent administration, unless otherwise specified.

5.1.1. Visit Windows

Unless otherwise specified, nominal visits will be used for all by visit analyses. The study visits scheduled after randomization should occur at the time delineated in the SoA.

5.1.2. Pooling Algorithm for Analysis Centers

Unless otherwise specified, data from all investigational centers/sites will be pooled for analyses.

5.1.3. Reference Date, Study Day and Relative Day

The Reference Date is the date of the first study agent administration. If the date of the first study agent administration is missing or the first study agent administration is not done, then the Reference Date equals the corresponding visit date (eg, Week 0 visit date). If the corresponding visit date is also missing, then the Reference Date equals the randomization date.

Study Day 1 or Day 1 refers to the reference date (there is no Study Day 0). All efficacy and safety assessments at all visits will be assigned a day relative to this date.

5.2. Participant Dispositions

Screened participants and reason for screen failures will be summarized overall.

The number of participants in the following disposition categories will be summarized throughout the study by intervention group and overall:

- Participants randomized
- Participants who received study intervention
- Participants who completed the study
- Participants who discontinued study intervention
 - Reasons for discontinuation of study intervention (including discontinuation due to COVID-19 related reasons)
- Participants who terminated study prematurely
 - Reasons for termination of study (including termination due to COVID-19 related reasons)

The above categories will include summaries through the end of study.

A listing of participants will be provided for the following categories:

- Participants who discontinued study intervention
- Participants who terminated study participation prematurely
- Participants who were unblinded during the study period
- Participants who were randomized but did not receive study intervention.

5.3. Primary Endpoint Analysis

Early Termination Note: Due to the Sponsor's decision to stop screening of new participants as a result of enrollment challenges, fewer than 60 participants will be enrolled in the study. The end of study will occur after all enrolled participants have completed the Week 20 visit or discontinued study intervention prior to Week 24, and all participants have completed their final efficacy and safety visits per the SoA.

For the CSR, the analysis of the primary composite estimand (Section 5.3.2.1) will be performed using the analysis method specified in Section 5.3.3. All other analyses that are described in this section will not be performed for the CSR.

5.3.1. Definition of Endpoint(s)

The primary endpoint is the proportion of participants achieving at least 50% decrease in proteinuria from baseline at Week 24. Proteinuria is based on UPCR.

Variable specific data handling rules: Observed data will be used for the analysis.

5.3.2. Estimands

Primary Trial Objective: To evaluate the efficacy of guselkumab in participants with active LN on standard-of-care.

Estimand Scientific Question of Interest: What is the proportion of participants considered to have benefited from guselkumab versus placebo for the pre-specified duration (24 weeks), administered together with the protocol-allowed background standard-of-care medication?

5.3.2.1. Primary Estimand (Composite Estimand)

a. **Study intervention:**

- Guselkumab (experimental treatment/intervention) in addition to standard-of-care
- Placebo in addition to standard-of-care

b. **Population:** Participants between 18 and 75 with active LN (defined by meeting the classification criteria for SLE by the 2019 European League Against Rheumatism (EULAR)/ACR, having a Class III or IV predominant kidney biopsy documentation of ISN/RPS proliferative nephritis within the last 6 months prior to or during screening despite receiving one or more standard-of-care treatments.

c. **Variable:** Responder binary variable, defined as a participant achieving at least 50% decrease in proteinuria from baseline at Week 24 who does not:

- discontinue study intervention for any reason excluding COVID-19 related discontinuations or
- meet the Medication Intercurrent Event in Section (e) below

d. **Summary measure (Population-level summary):** Difference in proportion between the study interventions

e. **Intercurrent events and their corresponding strategies:**

Intercurrent Events	Strategy for Addressing Intercurrent Events and Its Description
Discontinuation (DC) of study intervention for any reason excluding COVID-19 related discontinuations	Composite Strategy: A participant with this intercurrent event is considered to not have achieved at least 50% decrease in proteinuria after this event, the occurrence of this intercurrent event being captured in the variable definition.

Medication Intercurrent Event
 
 1. Exceeding baseline glucocorticoid dose 2. Increase above 10 mg/d prednisone equivalent after Week 12, use of new or increased dose of concomitant medication related to LN or other immunosuppressive agents, within 8 weeks prior to the endpoint 3. Initiation of prohibited medications at any time prior to the endpoint 
Note: adjustments in glucocorticoids are permitted up to and including Week 12. Nonsystemic glucocorticoids, NSAIDs, antimalarials and topical agents will not be considered an intercurrent event.
	
Composite Strategy: Same as above

--	---

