A participant receiving treatment for latent TB discontinues this treatment prematurely or is noncompliant with the therapy.

- The participant has a serious adverse reaction that is related to an injection or an infusion resulting in bronchospasm with wheezing and/or dyspnea that requires ventilatory support OR that results in symptomatic hypotension with a decrease in systolic blood pressure >40 mm Hg or blood pressure <90/60 mm Hg.
- The participant has a reaction resulting in myalgia and/or arthralgia with fever and/or rash (suggestive of serum sickness and not representative of signs and symptoms of other recognized clinical syndromes) occurring 1 to 14 days after an injection of study intervention. These may be accompanied by other events including pruritus, facial, hand, or lip edema, dysphagia, urticaria, sore throat, and/or headache.
- The participant has a malignancy including squamous cell skin cancer. Consideration may be given to allowing participants who develop ≤ 2 basal cell skin cancers that are adequately treated with no evidence of residual disease to continue to receive study intervention.
- Participant requires dialysis.
- Noncompliance with study drug administration defined as multiple episodes of missing the window in which to receive study intervention.
- The participant has severe liver test abnormalities that meet one of the conditions outlined in Appendix 11 (Section 10.11; Liver Safety: Suggested Actions and Follow-up Assessments).

The sponsor may elect to terminate the study at any time, and if the sponsor decides not to continue development for any reason, study medication/drug will no longer be provided to any participants, including those in the LTE.

Discontinuation of a participant's study intervention should be considered under the following conditions:

1. Persistent inadequate response or worsening of LN based on worsening of renal function.
2. If the participant initiates treatment with prohibited therapies for SLE or LN, the medical monitor or designee should be notified for possible discontinuation of study intervention (Section 6.5).
3. The participant develops a serious infection, including but not limited to sepsis or pneumonia.
Note: Any serious infection should be discussed with the medical monitor or designee, and study intervention should be withheld until the clinical assessment is complete.

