It is recognized that the major disruption involving Ukraine, Russia, and neighboring countries/territories may have an impact on the conduct of this clinical study due to, for example, isolation or quarantine of participants and study site personnel; travel restrictions/limited access to public places, including hospitals; study site personnel being unavailable, isolated, or reassigned to critical tasks.

The sponsor is providing options for study related participant management in the event of disruption to the conduct of the study. This guidance does not supersede any local or government requirements or the clinical judgement of the investigator to protect the health and well-being of participants and site staff. If, at any time, a participant's travel to the study site is considered to be dangerous, study participation may be interrupted, and study follow-up conducted. If it becomes necessary to discontinue participation in the study, the procedures outlined in the protocol for discontinuing study intervention will be followed.

If, as a result of the major disruption involving Ukraine, Russia, and neighboring countries/territories scheduled visits cannot be conducted in person at the study site, they will be performed to the extent possible remotely/virtually or delayed until such time that on-site visits can be resumed. At each contact, participants will be interviewed to collect safety data. Key efficacy endpoint assessments should be performed if required and as feasible. Participants will also be questioned regarding general health status to fulfill any physical examination requirement.

Every effort should be made to adhere to protocol-specified assessments for participants on study intervention, including follow up. Modifications to protocol-required assessments may be permitted after consultation with the participant, investigator, and the sponsor.

The sponsor will continue to monitor the conduct and progress of the clinical study, and any changes will be communicated to the sites and to the health authorities according to local guidance. Modifications made to the study conduct as a result of the major disruption involving Ukraine, Russia, and neighboring countries/territories should be summarized in the clinical study report.

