- Certain protocol-mandated visits to the study site may not be possible during the major disruption involving Ukraine, Russia, and neighboring countries/territories. Therefore, temporary measures may be implemented if considered appropriate by the sponsor and investigator to maintain continuity of patient care and study integrity. Certain measures, such as those listed below, may be necessary and should be instituted in accordance with applicable (including local) laws, regulations, guidelines, and procedures:
 - remote (eg, by phone/telemedicine) or in person, off-site (eg, in-home) interactions between site staff (or designees) and participants for study procedures eg, those related to safety monitoring/efficacy evaluation/study intervention storage and administration (including training where pertinent)

- study intervention administration may take place outside of the scheduled visit window, if the investigator determines this to be safe for the participant, due to disruption of study intervention shipment to the site
- laboratory assessments using a suitably accredited local laboratory
- Missed assessments/visits will be captured in the clinical trial management system for protocol deviations. Discontinuations of study interventions and withdrawal from the study should be documented in the electronic case report form (eCRF).
 - other relevant study data elements impacted by the major disruption involving Ukraine, Russia, and neighboring countries/territories should also be documented in eCRFs and/or other study systems, as directed by detailed sponsor guidance. These may include missed/delayed/modified study visits/assessments/dosing, and instances where temporary measures such as those above are implemented.
- The sponsor will evaluate the totality of impact of the major disruption involving Ukraine, Russia, and neighboring countries/territories on collection of key study data.
 - if needed additional data analyses will be outlined in study statistical analysis plan.

INVESTIGATOR AGREEMENT

I have read this protocol and agree that it contains all necessary details for carrying out this study. I will conduct the study as outlined herein and will complete the study within the time designated.

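### The primary estimand exempts COVID-19 stops but scores permanent stops forced by the Ukraine/Russia disruption as non-response, and no retained efficacy analysis would show the effect

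*SAP*

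**What the plan says.** **The rule.** In SAP 5.3.2.1 the responder variable requires that the participant does not "discontinue study intervention for any reason excluding COVID-19 related discontinuations". The section lists as an intercurrent event "Discontinuation (DC) of study intervention for any reason excluding COVID-19 related discontinuations". The strategy is composite: "A participant with this intercurrent event is considered to not have achieved at least 50% decrease in proteinuria after this event".

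**Where it recurs.** The same discontinuation event appears in the main estimands for:
- CRR at Week 24 (5.4.2.2.1)
- sustained steroid reduction (5.4.2.2.2.1)
- proteinuria response at Week 52 (5.4.2.2.3.1)
- CRR at Week 52 (5.4.2.2.4.1)
- the two UPCR thresholds (5.4.2.2.5 and 5.4.2.2.6)
- time to CRR (5.4.2.2.7.1)

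Treatment failure (5.4.2.1.5) is defined by the intercurrent events of Supplementary Estimand 5 (5.3.2.6), which use the same wording.

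**The disruption.** The protocol's guidance on the Ukraine/Russia disruption follows its reference list. It allows that "study participation may be interrupted, and study follow-up conducted" where travel is dangerous, and goes further: "If it becomes necessary to discontinue participation in the study, the procedures outlined in the protocol for discontinuing study intervention will be followed". Where shipment is disrupted, "study intervention administration may take place outside of the scheduled visit window", if the investigator judges this safe. On analysis it says: "if needed additional data analyses will be outlined in study statistical analysis plan".

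**What the SAP does with it.** Version 2.0 (16 August 2022) names COVID-19 in the estimands, in the disposition summary (5.2) and in the protocol deviations (Appendix 4). It mentions the disruption in none of them, and Appendix 2 records no changes to the protocol-planned analyses.

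**The concern.** The SAP has accepted that a stop with an external cause need not count as lack of efficacy, but it applies this to COVID-19 only and does not say why. Two participants can both stop for reasons unrelated to drug or disease. If the cause was COVID-19, the stop is exempt. If travel to the site had become too dangerous to continue, it is a non-response.

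At stake is non-response that carries no information about guselkumab. If such stops are balanced between arms, they pull the difference towards zero. If they are unbalanced, which is easy in a trial of fewer than 60, they can create or hide a difference. They enter the primary endpoint, seven secondary main estimands and time to treatment failure.

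**Working it through.** **1. Does the rule capture these stops?** The event is discontinuation of study intervention for any reason but one. The disruption is not that one. The guidance routes discontinued participation through the ordinary procedures for stopping study intervention, so a permanent stop meets the event and is scored as non-response from then on. An interruption, a remote or delayed visit, or a dose outside the window is not a discontinuation and does not meet it.

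**2. Would a retained analysis show the effect?** SAP 5.3 keeps only the primary composite estimand for the CSR. It drops Supplementary Estimand 2 (treatment policy), Supplementary Estimand 3 (event table limited to stops for worsening LN) and the tipping-point analyses. SAP 5.4 keeps only the main estimands, and 5.6, which uses treatment policy throughout, is dropped. Region is a model term, but Europe is a single stratum, and covariate adjustment cannot undo an outcome fixed by rule.

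**3. Can the stops be identified?** Protocol Appendix 12 requires a COVID-19 label on such discontinuations in the case report form. The disruption guidance asks only that discontinuations be documented in the eCRF.

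**4. What happens to an exempted stop?** The primary estimand gives COVID-19 stops no explicit strategy. Only Supplementary Estimand 4 (5.3.2.5) does, and it is dropped. SAP 5.3.1 and 5.3.3 imply that observed data are used and that a missing value stays missing. Protocol 9.4.2 counts missing data as non-achievement. On the protocol's reading, an exempted participant with no Week 24 UPCR is a non-responder anyway.

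**5. Illustrative size.** Inputs from SAP section 3: placebo response 49%, difference 30 points (so 79% on guselkumab), total 60 (30 per arm), one-sided alpha 0.10, stated power 89.84%.

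*Reproducing the plan's figure.* Summing binomial probabilities over all outcomes with 30 per arm for which the uncorrected z statistic exceeds 1.2816 gives 89.84%, as stated. The pooled normal approximation, used below, is

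power = Φ{[(p2 − p1) − 1.2816·√(2p̄(1 − p̄)/n)] / √[(p1(1 − p1) + p2(1 − p2))/n]}

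With p̄ = 0.64 and n = 30: (0.300 − 1.2816 × 0.1239)/0.1177 = 1.199, giving 88.5%.

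*Balanced stops.* Assume a share q of each arm stops because of the disruption, independently of outcome. Scored as non-response, each rate is multiplied by (1 − q), and so is the difference. Handled as missing, the rates stay and n becomes 30(1 − q). The documents give no value for q.

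| q | Rates if scored as non-response | Difference (points) | Power, scored as non-response | Power, handled as missing |
|---|---|---|---|---|
| 0 | 49.0% v 79.0% | 30.0 | 88.5% | 88.5% |
| 5% | 46.55% v 75.05% | 28.5 | 84.7% | 87.2% |
| 10% | 44.1% v 71.1% | 27.0 | 80.7% | 85.7% |
| 20% | 39.2% v 63.2% | 24.0 | 72.4% | 82.4% |

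Enrolment will be below 60 by an amount not given. At q = 10%, power is 67.9% against 73.4% with 20 per arm, and 58.8% against 64.1% with 15 per arm (scored as non-response against missing).

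*Unbalanced stops.* One would-be responder scored as a non-responder moves an arm's rate by 1/n: 3.3 points at 30 per arm, 6.7 at 15, 10.0 at 10. Someone who would not have responded moves nothing. The expected shift per stop at 15 per arm is therefore 0.79/15 = 5.3 points on guselkumab and 0.49/15 = 3.3 on placebo.

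**The case against.** **No commitment was broken.** The protocol promises further analyses only if needed, and the SAP's silence is compatible with a judgement that none was. A reader might infer that participants were affected and the result distorted. The documents do not show this: they give Ukraine-specific TB-testing text, but no count of participants in the region and no stop for this reason. This stands, and it limits what can be said about size.

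**The rule is narrower than it looks.** A reader might infer that anyone whose drug was delayed becomes a non-responder. That is not supported, because the guidance offers remote visits, interruption and late dosing, none of which is the intercurrent event.

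**The protocol does not plainly contradict itself.** Section 7.1 makes study intervention stop for "Noncompliance with study drug administration defined as multiple episodes of missing the window in which to receive study intervention", while the guidance allows out-of-window dosing under conditions. A reader might call this a contradiction. It can also be read as a general rule with a specific exception. What the text shows is that neither passage refers to the other, so a site cannot tell how repeated late doses under the guidance count.

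**An all-cause composite is legitimate.** This is true in general, but the SAP did not choose one. It exempted one external cause and gave no reason for stopping there.

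**The cases may be visible anyway.** SAP 5.2 summarises and lists reasons for discontinuation, and the guidance asks the CSR to summarise changes in conduct. That could reveal who stopped, if reasons are recorded specifically. It would not show the effect on the treatment difference.

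**Conclusion.** The point holds as a gap in the definition of the primary estimand, the secondary main estimands that repeat it, and treatment failure. A permanent stop forced by the disruption is scored as non-response or failure, an equivalent COVID-19 stop is not, and no retained efficacy analysis would show the difference. This conclusion rests on the text alone.

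The size is unknown and may be nil. The 27-point figure assumes 10% of each arm stop, independently of outcome, with the planning rates otherwise true. With balanced stops the bias is towards no difference; with unbalanced stops it can go either way. Nothing in the documents supports a claim that the trial's result is biased, or in which direction. The point is worth settling because the change is small and must be made before unblinding.

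**What to change.** 1. **SAP 5.3.2.1, each main estimand listed above, and the treatment failure definition through 5.3.2.6:** leave the COVID-19 exemption exactly as worded and add *or discontinuations related to the major disruption involving Ukraine, Russia and neighboring countries*. Narrowing the COVID-19 wording, for instance to logistical reasons, would turn stops for COVID-19 illness into non-responses, which nothing here justifies.
2. **State one strategy for both exempted causes.** For example, use observed Week 24 data and leave missing values to the model in SAP 5.3.3. Align this with protocol 9.4.2, since under its missing-data rule the exemption may change nothing. Record the departure from the protocol in SAP Appendix 2.
3. **Classify discontinuation reasons blind before database lock**, and add the category to the disposition summary in SAP 5.2. If there are no such stops, one sentence saying so closes the point.
4. **Reconcile protocol 7.1 with the disruption guidance** by cross-reference, so that the status of out-of-window doses given under the guidance is clear. Which provision governs is for the sponsor to decide.

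The cost is SAP wording, a protocol clarification and a blinded review of a short list. The downside is that a few participants may move from a fixed outcome to an observed or missing one.
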